### 11.2 Definition of Adverse Events

Adverse event means any untoward medical occurrence, such as an abnormal laboratory finding, physical sign, symptom, or diagnosis of a disease state, that is temporally associated with the use of an interventional treatment or procedure in a human subject regardless of whether or not it is considered intervention-related [consistent with 21 CFR 312.32 (a)].

### 11.2.1 Treatment-emergent AEs (TEAEs)

TEAEs are those that start or worsen after the start of study treatment and up to 7 days (for AEs) and 30 days (for serious AEs) after the last dose of study treatment. This AE definition would include the following:

- Any pre-existing condition that increases in severity or changes in nature during or as a consequence of the study treatment administration
- Complications resulting from protocol-mandated procedures
- AEs occurring as a result of product withdrawal, abuse or overdose
- A change in a laboratory variable if considered by the investigator to be clinically significant or if it is caused (or should have caused) the investigator to reduce or discontinue the use of the product or initiate a non-protocol therapy or procedure

### 11.2.2 AEs of Special Interest

AEs of Special Interest represent a specific subset of all AEs and are defined by the study protocol based on two distinct features: 1) their likely association with the investigational drug(s), and 2) the presence of pre-specified study drug management guidelines that are to be followed when the AE occurs.

AEs meeting the following criteria will be classified and reported as AEs of Special Interest in addition to their inclusion in the overall frequency and incidence of AEs.

- Leukopenia, defined as  $WBC \leq 2.5 \times 10^3/\mu\text{l}$  of blood
- Neutropenia, defined as an absolute neutrophil count  $< 1.0 \times 10^3/\mu\text{l}$  of blood
- Clinically significant anemia, defined as blood hemoglobin  $< 10.0 \text{ gm/dl}$  or a drop in hemoglobin to  $< 9.0 \text{ gm/dl}$  if the baseline hemoglobin was  $< 11.0 \text{ gm/dl}$
- Liver enzyme elevations that exceed  $3 \times$  the upper limit of normal (ULN) ALT and/or AST.
- New onset or worsening of existing gastrointestinal symptoms that do not respond to medical management and are of sufficient clinical importance to warrant drug dose adjustment (including nausea, diarrhea, vomiting, and dyspepsia).
- Documentation of gastrointestinal ulcer, gastrointestinal bleeding or abdominal emergency
- Infection requiring hospitalization, intravenous antibiotics, or judged as requiring the withdrawal of immune suppression for effective treatment.
- New or reactivated viral infections including PVAN, JC virus associated PML, CMV infections, reactivation of HBV or HCV.
- Photosensitivity skin reactions that do not respond to sunscreen, avoidance, and as-needed use of over the counter topical creams, and are of sufficient clinical importance to warrant drug dose adjustment.
- Development of a proven malignancy other than basal cell cancer of the skin or cervical carcinoma in situ removed entirely by biopsy.
- Angioedema

## 11.3 Definition of Serious Adverse Events (SAEs)

An AE or suspected adverse reaction is considered "serious" if, in the view of either the investigator or sponsor, it results in any of the following outcomes:

- Death,

- A life-threatening AE
- Inpatient hospitalization or prolongation of existing hospitalization
- A persistent or significant incapacity or substantial disruption of the ability to conduct normal life functions
- A congenital anomaly/birth defect.

Important medical events that may not result in death, be life-threatening, or require hospitalization may be considered serious when, based upon appropriate medical judgment, they may jeopardize the patient or subject and may require medical or surgical intervention to prevent one of the outcomes listed in this definition. Examples of such medical events include allergic bronchospasm requiring intensive treatment in an emergency room or at home, blood dyscrasias or convulsions that do not result in inpatient hospitalization, or the development of drug dependency or drug abuse. [Consistent with 21 CFR 312.32 (a)]

## 11.4 Definition of Unanticipated Problems (UP – unexpected AEs & Problems)

An AE or suspected adverse reaction is considered "unanticipated" if it is not listed or characterized in the Package Insert or in the current Investigator Brochure or is not listed at the specificity or severity that has been observed; or, if an investigator brochure is not required or available, is not consistent with the risk information described in the general investigational plan or elsewhere in the current application, as amended. For example, under this definition, hepatic necrosis would be unexpected (by virtue of greater severity) if the investigator brochure referred only to elevated hepatic enzymes or hepatitis. Similarly, cerebral thromboembolism and cerebral vasculitis would be unexpected (by virtue of greater specificity) if the investigator brochure listed only cerebral vascular accidents. "Unexpected," as used in this definition, also refers to AEs or suspected adverse reactions that are mentioned in the investigator brochure as occurring with a class of drugs or as anticipated from the pharmacological properties of the drug, but are not specifically mentioned as occurring with the particular drug under investigation. [Consistent with 21 CFR 312.32 (a)]

## 11.5 Classification of an Adverse Event

### 11.5.1 Severity of Event

The intensity of all AEs will be graded using a five-point grading scale in which the following descriptions of severity will apply. Note that for some AEs, Grades 4 and/or 5 may not be applicable. In those cases only 3 different grades (Grade 1-3) are to be considered:

8.2.1.1	Grade 1:	"Mild"; asymptomatic or mild symptoms; clinical or diagnostic observations only; intervention not indicated.
8.2.1.2	Grade 2:	"Moderate"; minimal, local or noninvasive intervention indicated; limiting age-appropriate instrumental ADL*.
8.2.1.3	Grade 3:	"Severe"; medically significant but not immediately life-threatening; hospitalization or prolongation of hospitalization indicated; disabling; limiting self care ADL**.
8.2.1.4	Grade 4:	"Life-threatening consequences"; urgent intervention indicated.
8.2.1.5	Grade 5:	"Death related to AE".

---

\*Instrumental ADL refer to preparing meals, shopping for groceries or clothes, using the telephone, managing money, etc.

\*\*Self care ADL refer to bathing, dressing and undressing, feeding self, using the toilet, taking medications, and not bedridden.

### 11.5.2 Relationship to Study Intervention

For all collected AEs, the clinician who examines and evaluates the participant will determine the AE's causality based on temporal relationship and his/her clinical judgment. A binary assessment (related/not related) will be made and take into consideration the natural history of the underlying disease, concurrent illness, concomitant therapy, study-related procedures, accidents, and other external factors. While the relationship to the study drug (related/not related) is part of the documentation process, it is not a factor in determining what is or is not reported in the study. All AEs are recorded regardless of relatedness.

Related	The AE is known to occur with the study agent, there is a reasonable possibility that the study agent caused the AE, or there is a temporal relationship between the study agent and event. Reasonable possibility means that there is evidence to suggest a causal relationship between the study agent and the AE. An AE can be deemed related even if other factors may have contributed to the event.
Not Related	There is not a reasonable possibility that the administration of the study agent caused the event, there is no temporal relationship between the study agent and event onset, or an alternate etiology has been established or appears to provide a plausible explanation (e.g. the participant's clinical condition, underlying disease or concomitant treatments).

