8.2.2 Relationship to Study Drug

For all collected AEs, the clinician who examines and evaluates the participant will determine the AE's causality based on temporal relationship and his/her clinical judgment. A binary assessment (related/not related) will be made and take into consideration the natural history of the underlying disease, concurrent illness, concomitant therapy, study-related procedures, accidents, and other external factors. While the relationship to the study drug (related/not related) is part of the documentation process, it is not a factor in determining what is or is not reported in the study. All AEs are recorded regardless of relatedness.

- 8.2.2.1 **Related** The AE is known to occur with the study agent, there is a reasonable possibility that the study agent caused the AE, or there is a temporal relationship between the study agent and event. Reasonable possibility means that there is evidence to suggest a causal relationship between the study agent and the AE. An AE can be deemed related even if other factors may have contributed to the event.
- 8.2.2.2 **Not Related** There is not a reasonable possibility that the administration of the study agent caused the event, there is no temporal relationship between the study agent and event onset, or an alternate etiology has been established or appears to provide a plausible explanation

(e.g. the participant's clinical condition, underlying disease or concomitant treatments).

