8.5 SAFETY OVERSIGHT

Safety oversight will be under the direction of a 3-member External Data and Safety Monitoring Board (DSMB, See Section 15.1.5) composed of individuals with the appropriate expertise in SSc-ILD, the study drugs and/or clinical trials research including experts in Rheumatology, Pulmonary Medicine, Internal Medicine and/or Bioethics, and Biostatistics. The DSMB Chair will be appointed by the Study Executive Committee from among experts in the field who are not otherwise actively involved in the conduct of the Clinical Study or its reporting or analysis and who do not have a salaried appointment with any of the participating institutions. The DSMB Chair will then recommend the remainder of the Committee Members for consideration by the study Executive Committee using similar expertise and affiliation criteria.

The DSMB will review the protocol and recommend modifications with respect to monitoring, safety and outcome assessments that will be addressed by the study prior to the onset of clinical activity. Once the trial is initiated, the DSMB will review cumulative trial results to evaluate the treatment for beneficial and adverse effects, including the review of all AEs, SAEs and UP. The board will also monitor the performance of individual clinics and study performance indicators (drug monitoring and compliance, visit compliance, recruitment, etc.). The DSMB will meet every 6 months by teleconference and/or web videoconferencing for the duration of the trial and will interact directly with the Data Coordinating Center for access to study data and interim reports, and with the Executive Committee regarding any recommendations for procedural changes, study modifications or management of perceived safety or data integrity issues.

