8.5.1 Morbidity and Mortality Committee

A separate Morbidity and Mortality Review Committee (MMRC) will be appointed by the Executive Committee and consist of the Medical Monitor and two invited members who are not otherwise involved in the research. The composition of the MMRC will include at least one member specializing in pulmonary medicine and one in rheumatology. The purpose of this committee will be to review all reported SAEs (as detailed in Sections 8.1 to 8.3) and provide an independent and blinded determination as to:

- a) The proximate cause of the SAE.
- b) Relationship of the SAE to the study drug as detailed in Section 8.2.2.
- c) The expectedness of the SAE as defined in Section 8.1.3.

Individual SAE case reports will be reviewed as they occur by an identified medical monitor who will assure that all relevant material has been collected and, in consultation with the reporting site investigator, that the determination of the proximate cause, relationship to the study drug and determination of expectedness are consistent with the documentation and reporting guidelines.

Independent reviews by the MMRC will occur retrospectively, in batches, at a time when the records for a group of 12-20 SAEs are ready for review or at the conclusion of the study if less than 12 SAEs are recorded. Each member of the MMRC will independently review cases and provide a determination. No further review will be required when all reviewers agree as to the relationship of the SAE to the study drug and the expectedness. Cases in which reviewers disagree on these determinations will be discussed at a MMRC teleconference and a final determination reported as either a consensus opinion (when all three reviewers agree after discussion) or a majority opinion (indicating the majority opinion of two out of three reviewers). The MMRC findings will represent the final study determination with respect to reporting SAE outcomes.

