## 11 Safety Analyses

Safety data, including AEs, clinical laboratory tests, vital signs, physical examinations, and concomitant medication usage will be summarized descriptively overall and by treatment group for the Safety Population. AEs include frequency of events and/or incidence of study subjects experiencing events, by study arm for the following:

- a) Study-defined treatment failures
- b) Study-defined treatment emergent AEs of special Interest
- c) All treatment-emergent AEs, total and by organ system classification
- d) All treatment-emergent AEs related to study medication, total and by organ system classification
- e) All treatment-emergent SAEs, total and by organ system classification
- f) All treatment-emergent SAEs related to study medication, total and by organ system classification
- g) All treatment-emergent AEs and SAEs that result in discontinuation of study medication
- h) Time to treatment failure
- i) Time to treatment-emergent AEs and SAEs resulting in premature discontinuation of study medication

For categorical safety outcomes, numbers and percentages will be used. For continuous safety outcomes, number, mean, standard deviation, median, interquartile range, minimum and maximum are used to summarize changes from baseline to each study visit in laboratory tests and vital signs. Percent change from baseline for laboratory values are summarized. The primary organ system associated with each adverse event was coded by the medical monitor. Kaplan-Meier methods are used to summarize graphically the time to treatment failure, and treatment-emergent AEs and SAEs that result in premature discontinuation of study medication.

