### 11.5.3 Expectedness

For all SAEs, the Clinical Site Principal Investigator, in consultation with a designated Medical Monitor whenever possible, will be responsible for determining whether the SAE is expected or unexpected using the definition from section 11.4 above.

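### The SAP takes SAE relationship from the site and omits the Morbidity and Mortality Review Committee, whose determination the protocol makes final

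*SAP*

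**What the plan says.** The protocol has two tiers.

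- **First tier, the site.** Protocol 8.2.2 covers all AEs: "For all collected AEs, the clinician who examines and evaluates the participant will determine the AE's causality". Protocol 8.2.3 gives SAE expectedness to the site principal investigator, consulting the medical monitor where possible.
- **Second tier, SAEs only.** Protocol 8.5.1 has the MMRC (the medical monitor and two invited members not otherwise involved in the research) review all reported SAEs. It decides proximate cause, relationship to study drug and expectedness, blinded, by agreement or by majority of three. The section concludes: "The MMRC findings will represent the final study determination with respect to reporting SAE outcomes".

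The SAP carries over the first tier only. SAP 11.5.2 repeats the site rule for causality: "the clinician who examines and evaluates the participant will determine the AE's causality based on temporal relationship and his/her clinical judgment". SAP 11.5.3 does so for expectedness: "For all SAEs, the Clinical Site Principal Investigator, in consultation with a designated Medical Monitor whenever possible, will be responsible". The committee does not appear anywhere in the SAP.

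Two planned results need SAE relationship. SAP 11 item f is "All treatment-emergent SAEs related to study medication, total and by organ system classification". SAP 5.2.2 item 10b, a secondary endpoint, counts participants with related treatment-emergent AEs by system organ class, and SAEs fall within that count. Neither names whose judgement is used.

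**The concern.** Anyone programming from the SAP finds one stated source for relationship, the examining clinician, and would use that field for SAEs too. The related-SAE summary would then differ in source from the determination that the protocol designates for reporting, with nothing in the SAP to show that a choice had been made.

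What is at stake is the secondary objective. Both documents ask whether the combination is well tolerated and free of limiting toxicity, and related SAEs are a direct part of that answer. The programme's own precedent is committee adjudication: Protocol 2.3.1.1.4 reports that SLS II SAE relatedness was decided by an independent committee, and draws its treatment comparison from those decisions.

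**Working it through.** There is no stated figure to reproduce. The check is a comparison of texts, followed by a bound on how much one event can matter.

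**1. Which tier governs which event**

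| Item | Protocol | SAP |
|---|---|---|
| Relationship, non-serious AE | Site clinician (8.2.2) | Site clinician (11.5.2): agrees |
| Relationship, SAE | Site first (8.2.2), MMRC final (8.5.1) | Site clinician only (11.5.2) |
| Expectedness, SAE | Site investigator first (8.2.3), MMRC final (8.5.1) | Site investigator only (11.5.3) |

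The documents differ in the last two rows.

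**2. Is the difference a recorded change?** SAP Section 14 lists nine changes, a to i. None concerns the MMRC or the source of SAE relationship.

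**3. Which results are touched**

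- SAP 11 item f: wholly, because it consists of related SAEs.
- SAP 5.2.2 item 10b: in part. Reclassifying an SAE changes the count only if that participant has no other related treatment-emergent AE in the same organ class. The SAE part of SAP 11 item d is affected in the same way.
- Expectedness: none of SAP 11 items a to i uses it.

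**4. Will every SAE have an MMRC finding when the analysis is run?** Protocol 8.5.1 reviews SAEs in batches of 12 to 20. Its only fallback is "at the conclusion of the study if less than 12 SAEs are recorded". If the total exceeds a full batch, no review point is stated for those left over. SAP 8.1 sets three conditions for the final analysis, and completion of MMRC review is not among them.

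**5. How much one event can matter.** The SLS II relatedness table in Protocol 2.3.1.1.4 gives:

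- Related SAEs: 3 on mycophenolate and 8 on cyclophosphamide, 3 + 8 = 11.
- All SAEs: 42 + 36 = 78. Share related: 11/78 = 14.1%.
- Effect of one reclassified SAE: 1/3 = 33% of the mycophenolate count, 1/8 = 12.5% of the cyclophosphamide count, 1/11 = 9.1% of the total.

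These figures are illustrative. The table's categories sum to 3 + 16 + 22 + 3 = 44 and 8 + 16 + 11 + 3 = 38, against stated totals of 42 and 36, so the categories overlap or contain errors.

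For this trial, the primary model in SAP 10.1 indexes 51 participants. On that number, one participant is 1/51 = 2.0 percentage points overall, or about 4 points in an arm of 25 or 26 if the arms are near equal. Arm sizes and the Safety Population count are not given.

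**The case against.** The strongest defence is that the SAP invented nothing. SAP 11.5.2 and 11.5.3 reproduce Protocol 8.2.2 and 8.2.3, the MMRC itself applies the 8.2.2 definitions, and SAP 4.1 says the SAP is to be read alongside protocol version 2.5, so 8.5.1 still applies. Item f names no source, and the table shells are in a separate document (SAP Section 16) that may name the right one. All of this stands, and it makes the defect an omission, not a new rule. It does not remove it: the SAP states one source for relationship, and for SAEs that is the superseded one.

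A reader might infer more, in four ways that the documents do not support.

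- **That site causality is wrong throughout.** It is not. The MMRC reviews SAEs only, so the site call is correct for non-serious AEs.
- **That the site call is unblinded.** Protocol 10.6.1 blinds study staff, apart from select coordinating-center staff and the research pharmacists. The MMRC adds independence and a three-member decision.
- **That reported expectedness would be wrong.** No listed analysis reports it.
- **That batching left the DSMB uninformed for several meetings.** The medical monitor, an MMRC member, reviews each SAE as it occurs. Protocol 10.4.7.1 puts SAEs before every DSMB meeting, and nothing it lists is split by relatedness. No DSMB decision is shown to wait on the MMRC. A count of meetings needs an SAE rate and an accrual time that are not given for this trial. For the trial as planned, assuming the SLS II mycophenolate rate, 42/(69 × 2) = 0.304 per person-year, and 150 participants entering evenly over 2 years, expected SAEs by year t are 0.304 × 150 × t²/4 = 11.4t². That reaches 12 at about month 12, after roughly two six-monthly meetings. SAP 8.5 also describes DSMB oversight as past, so rescheduling would change nothing now.

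**Conclusion.** Wrong as written, and it should be corrected. Protocol 8.5.1 makes the MMRC determination final for reporting SAE outcomes. The SAP omits it, so item f, and the SAEs within item 10b, would be built from the provisional tier.

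The size of the effect is unknown, because the documents give no rate of site-committee disagreement for either trial. It could be nil if the two always agree. The SLS II counts show only that related SAEs are few enough for one changed call to be visible. The conclusion on the source rests on the texts and on no assumed rate. It does assume that the separate table shells do not already name the MMRC, which cannot be checked here. The primary efficacy analysis is not affected.

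**What to change.** In the SAP:

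1. In Section 11 item f, 11.5.2 and 5.2.2 item 10b, state that for SAEs the relationship used is the MMRC determination under Protocol 8.5.1, and that the site determination is kept for non-serious AEs. Apply the same rule to the SAEs in Section 11 item d.
2. In 11.5.3, state that SAE expectedness, if reported, is the MMRC's.
3. In the SAE listing, show the site's assessment beside the MMRC's, so that any disagreement is visible.
4. In 8.1, add a condition that MMRC review of every recorded SAE, including any left after the last full batch, is complete before the final analysis.

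The cost is SAP wording, one listing column, and completing the review that the protocol already requires. No new data are needed from participants, and MMRC scheduling during the trial need not change.

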### 11.5.3 Expectedness

For all SAEs, the Clinical Site Principal Investigator, in consultation with a designated Medical Monitor whenever possible, will be responsible for determining whether the SAE is expected or unexpected using the definition from section 11.4 above.

### 11.5.4 Treatment Failures

Treatment failures are participants who, after >3 months of study, demonstrate

- an absolute fall in FVC-% of  $\geq 15\%$  from their baseline determination, or
- an FVC-%  $\leq 35\%$ , regardless of the absolute change from baseline.

To meet these definitions, participants must have two FVC-% measurements greater than 15 days apart, both showing an absolute decrement of  $\geq 15\%$  from baseline and/or a FVC-% of  $\leq 35\%$ . Participants with treatment failures will be withdrawn from active drug treatment (both PFD/Plac and MMF). Participants who fail treatment will be encouraged to return for key outcome determinations at 12 and 18 months.

